10.7.8 Safety Assessments

An assessment of adverse reactions and serious adverse events will be undertaken at each study visit from baseline to the last trial visit. These reviews will be carried out by the PI or other delegated staff member conducting the visit. Requirements for adverse event reporting are detailed fully in Section 11.

10.7.9 Resource Use Questionnaire

The University of Bangor will provide a resource use questionnaire for the trial's health economic outcomes. This may be completed by participants age 11 years or over, or parent/legal guardian of the participant if under 11 years of age [31].

Whilst the premise of this trial is to define the most effective treatment regimen as per the primary outcome, primary economic evaluation will determine the comparable cost effectiveness of the two treatments regimens.

Understanding the efficacy, safety and cost-effectiveness of oral vs IV will have the highest impact for the NHS and patients/families, as choices between these drugs are currently opinion and anecdotal rhetoric-based rather than evidence-based. The cost and impact on families is disproportionate between treating JIA with IV methylprednisolone and treating JIA with oral prednisolone. IV methylprednisolone is administered at an estimated cost of £1400 and involves cannulation and 3 days missed from school or work whilst oral prednisolone has an estimated cost of £7 per patient without any need for cannulation or missed school or work.

Benefits may also exist in terms of healthcare experience, longer-term outcomes or quality of life between the two corticosteroid regimens which will enable informed decisions with families about the choice of treatment. We will use our health economics analysis to inform NHS commissioning.

10.7.10 Paediatric Glucocorticoid Toxicity Index (pGTI) Assessment

The pGTI is a standardized, weighted clinical outcome assessment which measures change in glucocorticoid toxicity over time [18, 19]. It is an aggregate assessment of common, important glucocorticoid toxicities that are organized into health domains graded as minor, moderate, or major and weighted according to severity. Two quantitative scores comprise the overall toxicity profile derived from pGTI data: 1) the Cumulative Worsening Score; and 2) the Aggregate Improvement Score. The pGTI also includes a qualitative, unweighted record of glucocorticoid side-effects known as the Damage Checklist, which documents less common toxicities unlikely to change with varying glucocorticoid dosing. As part of this study, pGTI assessment data will be collected from participants at baseline, 6, 12, 24 and 52 weeks respectively and recorded on an electronic pGTI CRF developed by a third party company.

10.7.11 Tanner Puberty Stage Self-Assessment (included to support calculation of the pGTI scores)

The Tanner Puberty Stage Assessment [30] will be used to support the physician's confirmation of the participant's stage of puberty required for the physician's completion of the pGTI assessment. The Tanner Stage Puberty Assessment is a self-assessment questionnaire for assessing the onset of puberty in children [29, 30]. Children aged 10 and upwards will be asked to respond to questions regarding stage of puberty using pictures to support this. This assessment will only be done at baseline and 52 weeks.

10.8 Sample Management

10.8.1 Collection of standard care blood samples and bloods required for pGTI assessment

Participants will have blood tests as part of standard care and for pGTI calculation at every visit as shown in table 2. These will be ordered by the clinician who is examining the participant and taken by staff trained and competent to undertake venepuncture in accordance with site's policies and procedures. Please note it is acceptable, if a participant is randomised to IV arm, to collect baseline bloods at time of insertion of cannula for IV methylprednisolone administration.

10.8.1.1 Processing and analysis

Standard care and pGTI blood samples (LDL and HbA1c) will be processed and analysed at each site's hospital laboratories.

10.8.1.2 Recording of blood results

All blood results will be available in each participant's medical records however, only the actual results from ESR, LDL and HbA1C blood tests should be recorded on the appropriate CRF at every visit.

The clinician who examines the participant will be responsible for monitoring the participant's blood results as well as responding to and reporting clinically significant abnormal results in accordance with section 11.

The schedule for standard care blood tests can be found in the Schedule of Events in section 10.7.1

10.8.1.3 Volume of blood to be collected

For participants age 16yrs and under, the maximum volume of blood collected for standard care blood tests and research-specific blood tests will be a maximum of 12mls.

For participants over 16 years, the maximum volume of blood collected for standard care blood tests and research-specific blood tests will be a maximum of 15mls.

10.8.2 Collection and shipment of blood samples for future research (OPTIONAL)

Participants and where appropriate, their legal guardian(s), will be provided with written information to explain that, as part of this study, participants are invited to provide blood samples at the baseline visit and 3 month visit for future research. Participants can still take part in the clinical trial if they do not consent/assent to blood samples being taken for future research. This includes a one-off DNA sample (ideally at baseline but can be taken at any time during the study) and samples for serum and PBMCs at baseline and 12 weeks. If a sample cannot be taken at baseline or the 3month visit, participants should be asked if they are willing to provide it at a later visit. Written informed consent (with assent where appropriate) will be sought. Blood samples for future research will be collected where consent/assent is obtained and deposited into the Liverpool University Biobank (LUB). A detailed description of sample collection, packaging and shipping is provided in the STAR-JIA Sample Collection Manual. In brief, samples will be collected at trial sites using pre-labelled sample collection kits, blood will be posted to the Liverpool University Biobank where they will be processed to plasma, red cell pellet, serum and PBMCs and where required to protein and nucleic acids.

A detailed description of processes for sample collection, packaging, shipment and ordering kits is provided in the STAR-JIA Sample Collection Manual. Samples should be collected as early in the day as possible to allow for next day delivery to the Liverpool University Biobank (LUB). If possible, arrange blood sample collection times between Monday and Thursday to avoid deliveries over the weekend when lab staff will not be available to process samples. For enquiries regarding samples collected for future research, please email LUB at: [contact] or telephone LUB on: **[name]**.

10.8.3 Custodianship

The optional blood samples collected as part of the STAR-JIA trial will be considered as a gift and adopted by Liverpool University Biobank and stored for release to researchers for future approved research.

10.9 Intervention Discontinuation and Participant Discontinuation / Withdrawal

In consenting to the trial, participants / Legal Representatives agree to all trial activities including administration of trial intervention and treatment and follow-up assessments, visits and data collection. Every effort should be made to facilitate the completion of these for every recruited participant. If it is not possible to complete these activities (or it is deemed inappropriate) the reasons why should be documented. The following sub-sections describe the different levels of discontinuation/withdrawal.

10.9.1 Premature Discontinuation of Trial Intervention

Participants may discontinue treatment for reasons including, but not limited to:

- Participant-led, i.e. request by the participant / Legal Representative
- Unacceptable side effects (see Section 11 for Adverse Event reporting)
- Clinician-led:
 - Any change in the participant's condition that justifies the discontinuation of treatment in the clinician's opinion.
 - Participant meets an exclusion criterion (either newly developed or not previously recognised)

10.9.2 Premature Trial Intervention Discontinuation Procedures

Discontinuation from trial intervention should be reported to LCTC using the 'Premature Discontinuation of Trial Intervention' CRF. This does not mean discontinuation of the trial altogether, and the remaining trial procedures, follow up visits and data collection should be completed as indicated in the protocol (unless consent is specifically withdrawn). Data to be collected at the time of discontinuation will include the following:

- Reason for the premature trial intervention discontinuation should be documented on the appropriate CRF.
- All baseline data will be collected and should have already been completed on the appropriate CRF.
- All queries relating to baseline data should be dealt with within two weeks of being raised.
- The participant should be asked if are happy to remain in this trial.
- LCTC should be informed if a participant requests to withdraw from this trial.

10.9.3 Participant Withdrawal

Participants / Legal Representatives are free to withdraw at any time without providing a reason, though a reason should be recorded if one is given. LCTC should be informed via email to the LCTC and via completion of a Withdrawal CRF to be returned to LCTC within 7 days.

If participants / Legal Representatives express a wish to withdraw from further trial activities, the research team at site should ascertain if this is for all elements of trial follow-up, or if for example data from routine assessments can still be collected for the trial. In the case of ongoing adverse events, participants should be given appropriate care under medical supervision until the symptoms of any adverse event resolve or the patient's condition becomes stable.

Where a participant / Legal Representative decides that they do not want any further data to be provided for trial purposes, data already collected up to the point of withdrawal will still be used in trial reports and analyses, but no further data will be collected unless required by law (e.g. safety reporting regulatory requirements).

10.9.4 Participant Transfer

If a participant moves from the area, every effort should be made for them to be followed-up at another participating trial site and for this trial site to take over responsibility for the participant.

A copy of the participant's CRFs should be provided to the new site. The participant remains the responsibility of the original site until the new site PI has signed the Transfer CRF.

10.9.5 Loss to Follow-up

A participant will be considered lost to follow up if they fail to return for three scheduled visits and are not contactable by the site research team.

If a participant fails to attend/facilitate a required trial visit the following actions must be taken:

- Site will attempt to contact the participant and reschedule the missed visit (be conscious of acceptable windows for collecting valid data) and advise the participant on the importance of maintaining the assigned visit schedule.
- Before a participant is deemed to be lost to follow up, site research staff will make every effort to regain contact with the participant (i.e. three telephone calls and, if necessary, a headed letter to last known address). These efforts should be recorded in the participant's medical notes.)
- If the participant continues to be unreachable, they should be considered withdrawn from the trial with a primary reason of lost to follow up and this should be recorded on the appropriate CRF.

10.10 End of Trial

The End of the Trial is defined to be the database lock. Trial closure activities will begin once all participant treatment and follow-up are complete. Alternatively, the trial may be closed prematurely by the TSC, on the recommendation of the IDSMC. Site and trial closure activities will be centrally coordinated and conducted in accordance with LCTC processes regardless of whether the trial closes as planned or prematurely.

10.10.1 Trial Discontinuation

In the event that the study is discontinued, all participants will be followed-up post treatment and adverse events will continue to be collected as per protocol (see section 9). The treating clinician will be responsible for deciding the best treatment locally for each participant.

11 SAFETY REPORTING

Safety reporting in clinical trials is a legal and ethical requirement and it is imperative that all applicable requirements detailed here are followed during the trial.

For the purposes of this study, Adverse Reactions (AR) related to the interventions, IV methylprednisolone and oral prednisolone and JIA-related Uveitis and **all** Serious Adverse Events (SAEs) are reportable.

ARs will be collected at 6 weeks and 12 weeks **only** due to the short half-life of corticosteroids and that most adverse reactions occur whilst on or shortly after stopping corticosteroids.

All Serious Adverse Events (SAEs) will be recorded throughout the study and must be reported immediately (and within 24 hours of knowledge of the event) by entry into the trial database and signed off by the PI.

This includes SAEs related to IMPs and Non-Investigational Medicinal Products (NIMPs). Any trial specific SAE reporting exceptions are detailed in section 11.4.

11.1 Terms and Definitions

Adverse Event (AE)	Any untoward medical occurrence in a patient or clinical trial subject administered a medicinal product and which does not necessarily have a causal relationship with this treatment. An AE can therefore be any unfavourable and unintended sign (including an abnormal laboratory finding, for example), symptom or disease temporally associated with the use of a medicinal product, whether or not considered related to the medicinal product.
Adverse Reaction (AR)	Any untoward and unintended response to an investigational medicinal product related to any dose administered.
Serious Adverse Event (SAE)	Any untoward medical occurrence or effect that at any dose results in death, is life-threatening, requires hospitalisation or prolongation of existing hospitalisation, results in persistent or significant disability or incapacity, or is a congenital anomaly or birth defect.
Serious Adverse Reaction (SAR)	An adverse reaction which meets the definition of serious (see Section 11.3) is a SAR. A SAR event that has been assessed as 'expected' (see Section 11.7 Expectedness) according to the Reference Safety Information (see below) will remain classified as a SAR only, however some Serious Adverse Reactions that are considered 'unexpected' will be further classified as a Suspected Unexpected Serious Adverse Reaction (SUSAR) (see below).

Suspected Unexpected Serious Adverse Reaction (SUSAR)	An adverse reaction that is classed in nature as serious and “unexpected” (i.e. not listed within the Reference Safety Information (RSI) approved for the trial by the MHRA and current at the time of onset of the SUSAR).
--	---

11.2 Adverse Events

Only adverse events that meet the definition of seriousness are reportable see section 11.3

11.3 Assessment of “Seriousness”

The assessment of seriousness of safety events must be performed by an appropriately delegated, medically qualified member of the site research team.

An Adverse Event or Adverse Reaction is assessed as serious if it:

- Results in death.
- Is life-threatening.
 - (i.e. the investigator considers the event places the subject at immediate risk of death from the experience as it occurred (this does not include an adverse experience that, had it occurred in a more severe form, might have cause death)
- Requires hospitalisation or prolongation of existing hospitalisation.
 - (hospitalisation is defined as an inpatient admission, regardless of length of stay, even if the hospitalisation is a precautionary measure for continued observation. Hospitalisations for a pre-existing condition, including elective procedures that have not worsened, do not constitute an SAE)
 - The above excludes admission to a Day Unit for treatment.
- Results in persistent or significant disability or incapacity.
 - (i.e. substantial disruption of one’s ability to conduct normal life functions)
- Consists of a congenital anomaly or birth defect.
 - (in offspring of subjects, or their partners, taking the IMP regardless of time of diagnosis)
- Is another important medical event.
 - (these may not result in death, be life-threatening, overdose, secondary malignancy or require hospitalisation, but may be considered a serious adverse event/experience when, based upon appropriate medical judgment, they may jeopardise the subject and may require medical or surgical intervention to prevent one of the outcomes listed in this definition).

11.4 Trial Specific SAE Reporting Requirements

SAEs must be entered into the trial database within 24 hours of the site becoming aware.

11.5 Severity of Adverse Events

All adverse events should be assessed for severity. The assignment of the severity/grading should be made by the investigator (or medically trained delegate) responsible for the care of the participant using the definitions in the table below.

Table 2: Severity Grading

Severity	Description
----------	-------------

Mild	Does not interfere with routine activities
Moderate	Interferes with routine activities
Severe	Impossible to perform routine activities

N.B. A distinction is drawn between **serious** and **severe** AEs. Severity is a measure of intensity (see above) whereas seriousness is defined using the criteria in Section 11.3). Hence, a severe safety event need not necessarily be a “serious” safety event.

11.6 Assessment of “Causality” - Relationship to Trial Treatment/Intervention

The assessment of the causality should be made by the investigator responsible for the care of the participant using the definitions in the table below. Assessment should be made against the IMP or comparator administered to a participant.

Table 3: Definitions of Causality

Relationship	Description
Unrelated	There is no evidence of any causal relationship. N.B. An alternative cause for the AE should be given.
Unlikely	There is little evidence to suggest there is a causal relationship (e.g. the event did not occur within a reasonable time after administration of the trial medication). There is another reasonable explanation for the event (e.g. the participant’s clinical condition, other concomitant treatment).
Possibly	There is some evidence to suggest a causal relationship (e.g. because the event occurs within a reasonable time after administration of the trial medication). However, the influence of other factors may have contributed to the event (e.g. the participant’s clinical condition, other concomitant treatments).
Probably	There is evidence to suggest a causal relationship and the influence of other factors is unlikely.
Almost certainly	There is clear evidence to suggest a causal relationship and other possible contributing factors can be ruled out.

Events that are assessed as being possibly, probably or almost certainly related will be classed as “Related” (i.e. having a reasonable possibility of being a causal relationship), and events assessed as unrelated or unlikely will be classed as “Unrelated” (i.e. having no reasonable possibility of being related).

Assessment of causality should be made based on known safety profiles of the IMPs in question (e.g. SmPC) or of other drugs in the same class.

In the case of discrepant views on causality between the treating investigator and others, **the causality assessment of the treating investigator will never be downgraded** and the MHRA & REC will be informed of both points of view.

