6.1.2 Secondary Objective(s)

- 2) To compare the differences in JIA Core Outcomes [15] for intravenous methylprednisolone versus oral prednisolone for the following domains:
 - a. Pain
 - b. Function
 - c. Health-related Quality of Life (HRQOL)
- 3) To assess the effectiveness of intravenous versus oral corticosteroids in minimising the need for additional treatments including all corticosteroid routes and additional disease-modifying anti-rheumatic drugs (DMARDs)/biologics.
- 4) To evaluate short/medium term safety and tolerability of IV versus oral corticosteroids, with regards to adverse reactions, serious adverse events, laboratory assessments and paediatric glucocorticoid toxicity index (pGTI).
- 5) To determine if a dose response relationship can be identified in the efficacy/adverse responses to corticosteroids across all participants by secondary analysis, normalising corticosteroids received for dose, bioavailability and potency using previously published data.

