11.9 Notes on Safety Event Recording

The following events must be recorded for the purposes of the trial:

- An exacerbation of a pre-existing illness
- An increase in frequency or intensity of a pre-existing episodic event/condition
- A condition (even though it may have been present prior to the start of the trial) detected after trial drug administration
- Continuous persistent disease or symptoms present at baseline that worsens following the administration of the trial treatment
- Laboratory abnormalities that require clinical intervention or further investigation (unless they are associated with an already reported clinical event)

- Abnormalities in physiological testing or physical examination that require further investigation or clinical intervention
- Injury or accidents
- Pregnancy (See section 11.10 for more details)

Do not record:

- Non-related Adverse Events
- Medical or surgical procedures - the condition which leads to the procedure is the adverse event
- Pre-existing disease or conditions present before treatment that do not worsen
- Situations where an untoward medical occurrence has occurred e.g. cosmetic elective surgery
- Overdose of medication **without signs or symptoms**
- The disease being treated or associated symptoms/signs unless more severe than expected for the participant's condition

*N.B. If overdose occurred **with** resulting signs and symptoms that meet the protocol criteria for SAE (i.e., requiring hospitalisation) then they should be reported accordingly (see section 11.4 for more information) and the overdose highlighted to the LCTC team.

The events above do not need recording as the trial is considered low risk. Both the IMP and Comparator are given in standard care for new onset pJIA. This is documented in the Risk Assessment.

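### The protocol does not say whether non-serious harms of giving the IV drug count as adverse reactions, and its recording rules conflict, so the IV-versus-oral tolerability comparison may miss them

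*Protocol*

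**What the plan says.** Objective 4 in Protocol 6.1.2 reads: "To evaluate short/medium term safety and tolerability of IV versus oral corticosteroids, with regards to adverse reactions, serious adverse events", followed by laboratory assessments and the pGTI. Adverse reactions are therefore one of four named measures of tolerability.

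Section 11.1 defines an adverse reaction as "Any untoward and unintended response to an investigational medicinal product related to any dose administered". Section 11.6 sets the reference for causality, "Assessment should be made against the IMP or comparator administered to a participant", and its basis: "Assessment of causality should be made based on known safety profiles of the IMPs in question".

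On recording, 11.2 makes only serious adverse events reportable. The do-not-record list in 11.9 includes "Non-related Adverse Events" and also "Medical or surgical procedures - the condition which leads to the procedure is the adverse event". Section 11.12.1 says the opposite: the PI must see that all adverse events reach the CRF, irrespective of seriousness, relatedness or expectedness, and that they are entered within 7 days.

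Outside the safety section, the protocol treats delivery as part of the IV burden. In 10.7.9, IV treatment "involves cannulation and 3 days missed from school or work", and 5.1 makes the same point when justifying the comparison. No safety passage says how a harm of cannulation or of the infusion procedure is to be classified.

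**The concern.** When the trial question is route of administration, what the route does to the patient is part of the intervention. The definition and the causality rule refer to the drug. A failed cannulation, or an infection where the cannula sat, is most naturally explained by the procedure, so an investigator following the text closely could call it unrelated. It would then not be an adverse reaction and, under 11.9, might not be recorded at all.

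Only the IV arm is cannulated to receive trial treatment, on 3 consecutive days. If such events are dropped, the loss falls on one arm and makes IV look better tolerated than it was. If sites read the rule differently, the comparison also mixes two definitions across at least 14 centres. Analysis cannot recover events that were never collected.

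**Working it through.** This is mainly a question of reading the rules together. Take a non-serious phlebitis or infection at the cannula site in an IV participant.

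1. *Is it an adverse reaction?* Under 11.1 it must be a response to the medicinal product. The text does not mention the procedure.
2. *Is it related?* Table 3 in 11.6 allows two answers. An event with another reasonable explanation is Unlikely, which counts as unrelated; the cannula is such an explanation. An event soon after administration to which other factors may have contributed is Possibly, which counts as related. Both descriptions fit.
3. *Is it recorded if judged unrelated?* Under 11.2 and 11.9, no. Under 11.12.1, yes.
4. *Does recording it under 11.12.1 bring it into objective 4?* Not by itself. That objective names adverse reactions and serious adverse events. A non-serious event recorded as unrelated is neither.
5. *Does another objective 4 measure pick it up?* The serious-event route takes serious cases only. The pGTI (10.7.10) grades glucocorticoid toxicity. The laboratory assessments are blood tests.
6. *What about failed cannulation?* It precedes the first dose, while active monitoring in 11.8 starts with IMP administration, so it may fall before the window opens.

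The gap thus has two parts: classification (steps 1, 2 and 4) and recording (step 3). Resolving only the recording conflict leaves classification open.

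**Size.** The protocol gives no rate of adverse reactions or procedure harm, so there is no figure to reproduce. The following shows direction and scale on assumed rates only.

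Inputs: 130 participants at 1:1, so 130 / 2 = 65 per arm (12.1.1 and section 7). Assumed: drug-reaction risk b, equal in both arms, at 20%, 30% or 40%; an independent IV-only procedure-harm risk q at 5% to 30%.

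IV risk if procedure harms are counted = 1 − (1 − b)(1 − q). Relative risk = that value / b. If they are all omitted, relative risk = b / b = 1.00.

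| q | IV participants affected (65 × q) | RR, b = 20% | RR, b = 30% | RR, b = 40% |
|---|---|---|---|---|
| 5% | 3.25 | 0.24/0.20 = 1.20 | 0.335/0.30 = 1.12 | 0.43/0.40 = 1.075 |
| 10% | 6.5 | 0.28/0.20 = 1.40 | 0.37/0.30 = 1.23 | 0.46/0.40 = 1.15 |
| 20% | 13 | 0.36/0.20 = 1.80 | 0.44/0.30 = 1.47 | 0.52/0.40 = 1.30 |
| 30% | 19.5 | 0.44/0.20 = 2.20 | 0.51/0.30 = 1.70 | 0.58/0.40 = 1.45 |

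These are upper limits on the distortion at each pair of rates, because they assume that every such event is omitted. Partial recording gives something in between.

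**The case against.** A reader might infer that the rules exclude every non-serious procedure harm, and that objective 4 is therefore biased towards IV by construction. The documents do not support that, for these reasons:

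- 11.12.1 requires unrelated events to be recorded, so the recording rule is contradictory rather than settled against them.
- The introduction to section 11 and the title of 11.6 speak of interventions, which an investigator may take to include delivery.
- An event judged Possibly related counts as related, and 11.6 forbids downgrading the treating investigator's view. Phlebitis at an infusion site can reasonably be placed there. Whether the product information lists site reactions cannot be checked from the protocol.
- The must-record list in 11.9 includes injuries, and examination abnormalities that need intervention, with no causality condition on those lines.
- All serious adverse events are captured whatever their cause, and a reaction to the infused drug is an adverse reaction as defined.
- Bruising and needle distress are not confined to IV. Both arms have blood taken at every visit (10.8.1), and methotrexate may be given subcutaneously in either (9.10.3).
- If a procedure problem stops treatment, the reason goes on the discontinuation CRF (10.9.2).

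All of this stands, and it limits the point to cannula- and infusion-procedure harms that are non-serious. It does not remove it. The broader wording permits inclusion without requiring it, and an event recorded as unrelated remains outside the adverse-reaction comparison.

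**Conclusion.** The concern holds as an ambiguity joined to a contradiction. Sections 11.1 and 11.6 do not say whether relatedness covers administration, and 11.2 and 11.9 conflict with 11.12.1. As written, sites may leave non-serious cannula- or infusion-procedure harms out of the adverse-reaction comparison, and may differ in doing so. For harms specific to the cannula or infusion procedure, any omission favours IV.

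The direction follows from the design. The size does not follow from anything in the protocol: the relative risks of 1.075 to 2.20 rest wholly on assumed rates, equal drug-reaction risk, independence and complete omission. The documents support neither a stated number of lost events nor a claim that all of them are lost. The primary outcome is unaffected. This is a cheap and worthwhile improvement to a secondary comparison that matters in a route-of-administration trial.

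**What to change.** - Reconcile 11.2 and 11.9 with 11.12.1, so that there is one rule on which non-serious events are recorded.
- State in 11.1 and 11.6 that, for the objective 4 comparison, relatedness is judged against the allocated intervention including its administration. Apply this alike in both arms: cannulation and infusion for IV, taking the tablets or solution for oral.
- List administration-related events as recordable in 11.9, and say whether those occurring before the first dose are included.
- Add one CRF field separating drug from administration procedure as the attributed cause, and report both by arm.
- Keep SAR and SUSAR classification on drug-related events, so that regulatory reporting does not change.

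The cost is protocol wording and one CRF field, with minor extra recording that can be completed at the existing week 6 visit. The event count in the IV arm may be slightly higher. No extra visits or procedures are needed.
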